2.1. Study Rationale

Inflammatory bowel disease (IBD) is a term used to describe 2 idiopathic conditions characterized by chronic inflammation of the gastrointestinal tract: Crohn's disease and ulcerative colitis (UC). In patients with UC, mucosal inflammation and ulceration occurs in the rectum and can extend proximally to a portion of or to the full colon, resulting in symptoms and signs such as abdominal pain, bloody stool, diarrhea, urgency to defecate, fatigue, nausea, loss of appetite, weight loss, fever, and anemia.

Initial therapy for UC generally includes the anti-inflammatory drugs 5-aminosalicylates and corticosteroids. Immunomodulators (e.g., methotrexate, azathioprine, and 6-mercaptopurine) may subsequently be used to maintain remission and avoid long-term corticosteroid use. However, these treatments often fail to control the disease long-term, particularly in patients with moderately to severely active UC, and both the corticosteroids and the immunomodulators can produce significant side effects.

The introduction of biologic agents has improved the therapeutic options for patients with moderately to severely active UC. Approved biologics include tumor necrosis factor alpha (TNF- α) antagonists (infliximab, adalimumab, certolizumab, and golimumab), the anti- $\alpha 4\beta 7$ integrin monoclonal antibody vedolizumab (██████), and the anti-interleukin 12/23 monoclonal antibody ustekinumab (██████). Other therapeutic options recently approved for the treatment of UC are Janus kinase (JAK) inhibitors, such as the small molecule tofacitinib (██████) or upadacitinib (██████). Despite this increase in therapeutic options for the treatment of UC, the percentage of patients with moderately to severely active UC who do not respond to induction therapy is still substantial, and the durability of response is low. For example, in Phase 3 studies in patients with moderately to severely active UC, adalimumab treatment achieved clinical remission at 8 weeks in 18.5% of patients and maintained remission in 8.5% at 52 weeks (██████ package insert). Thus, there remains an unmet need for more effective therapies for UC.

The pathogenesis of IBD is associated with activation of immune cells and their trafficking into the gut and the surrounding tissue to promote chronic inflammation. The integrin $\alpha 4\beta 7$ is required by immune cells to facilitate trafficking from the bloodstream to mucosal tissues, including the gut. This is achieved through binding of the $\alpha 4\beta 7$ integrin on immune cells to its cognate ligand, MAdCAM-1, expressed on the endothelial vessels within close proximity to mucosal tissues. Importantly, the $\alpha 4\beta 7$ integrin is employed by immune cells in the pathogenesis of IBD; therefore, inhibiting $\alpha 4\beta 7$ blocks the entry of immune cells into mucosal tissue, thereby alleviating the inflammation associated with IBD in many patients. Thus, the $\alpha 4\beta 7$ integrin is an ideal therapeutic target for selectively blocking inflammation of the gastrointestinal tract while minimizing effects in other organs (Fedyk, 2012). Inhibition of $\alpha 4\beta 7$ is a validated mechanism for the treatment of IBD, as demonstrated by vedolizumab (██████), a monoclonal antibody administered via intravenous infusion.

MORF-057 is a small molecule designed to selectively inhibit integrin $\alpha 4\beta 7$. It is currently being developed as an oral therapy for UC because vedolizumab, which has the same mechanism of action, has demonstrated efficacy in patients with UC who have moderately to severely active

disease. Relevant data from all non-clinical and clinical studies in the MORF-057 development program are provided in the current Investigator's Brochure (IB).

The aim of the current MORF-057-202 study is to evaluate the efficacy and safety of 3 active dose regimens of MORF-057 (as capsule, by mouth [P.O.]) versus placebo in study participants with moderately to severely active UC. Data from the MORF-057-202 study will provide further information to advance the clinical development program of MORF-057 for the treatment of UC.

2.2. Background

Inhibition of $\alpha_4\beta_7$ integrin is an important therapeutic goal for the treatment of moderately to severely active UC that has been clinically validated with the monoclonal antibody vedolizumab (████████). MORF-057 is an orally administered small molecule designed to selectively inhibit integrin $\alpha_4\beta_7$. It prevents MAdCAM-1 from binding to the $\alpha_4\beta_7$ integrin via a competitive mechanism (Yu, 2012). There are several potential clinical advantages of using MORF-057 (an orally administered drug) for the treatment of UC over vedolizumab (a drug administered via intravenous infusion), which uses the same mechanism of action. These advantages include a flexible dosing regimen and minimal safety concerns regarding immunogenicity and serious infusion reactions, requiring fewer clinical visits and therefore reducing patient and healthcare provider burden. MORF-057 has the potential to be an effective and safe oral $\alpha_4\beta_7$ integrin inhibitor that would be an important addition to the therapeutic armamentarium for UC.

A detailed description of the chemistry, pharmacology, and safety of MORF-057 is provided in the current IB. Important non-clinical and clinical study results are summarized below.

2.2.1. Non-clinical Findings

Non-clinical studies have demonstrated that MORF-057 is highly selective for $\alpha_4\beta_7$ over other integrins by a range of >100-fold to 143,000-fold. In addition, in a monkey gut homing model, MORF-057 blocked gut homing of $\alpha_4\beta_7$ -positive T-cells into lymphoid tissue, as measured by frequency of lymphocytes in tissue and in circulating blood as biomarkers, suggesting MORF-057 can inhibit an established and important mechanism involved in the pathogenesis of IBD.

MORF-057 has been characterized in Good Laboratory Practice-compliant toxicity and safety studies. MORF-057 had no effect on respiration, neurobehavior, or cardiovascular function, and had no genotoxicity or phototoxicity potential. Potential toxicity risks based on non-clinical data include effects to the stomach, liver, hematopoietic system, and embryo-fetal development.

See the current MORF-057 IB for additional details.

For human doses of 100 or 200 mg twice a day (B.I.D.), the calculated safety margin based on the no observed adverse effect levels (NOAELs) for the gastric changes identified in the 26-week study (50 mg/kg/day) is 8.2 -fold or 4.1-fold, respectively. Likewise, the exposure multiple based on the NOAEL observed in dogs in the 39-week study (300 mg/kg/day) is 190.2-fold or 95.6-fold for the 100 or 200 mg B.I.D. doses, respectively. The exposure margin based on a dose (60 mg/kg) that caused non-adverse minimal elevations of liver transaminases (alanine transaminase [ALT] 1.24 x) in dogs dosed for 39 weeks is approximately 20-fold for the 100 mg B.I.D. and 10-fold for the 200 mg B.I.D. doses. The safety margin based on the embryo-fetal NOAEL in rabbits (50 mg/kg/day) is 0.8-fold or 1.6-fold for the 100 or 200 mg B.I.D. doses, respectively (refer to Section 4 of the current IB for details).

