2.3.2. Risks

2.3.2.1. Risks of MORF-057

Overall, based on the available data for MORF-057 to date, the risk to study participants is expected to be minimal.

Potential toxicity risks based on MORF-057 non-clinical data include effects to the stomach, liver, hematopoietic system, and embryo-fetal development. The gastric, hepatic, and hematopoietic findings demonstrated partial or complete reversibility and are generally clinically monitorable.

Phase 1 DDI studies indicate that MORF-057 is a weak inducer of CYP3A. Sensitive CYP3A substrates for which small decreases in exposure can result in an unacceptable decrease in efficacy should be used with caution. In particular, systemic hormonal contraception should not be considered reliable and should not be used for the purpose of contraception.

Based on available clinical data from both completed and ongoing studies, there are no anticipated risks of particular severity that require monitoring beyond the routine monitoring typically associated with integrin receptor antagonists or other immunomodulatory products in human studies.

Safety precautions that will be taken during the study are listed below:

- Safety assessments and monitoring will be performed throughout the study, including evaluating the incidence of TEAEs, as well as abnormalities in clinical laboratory values, vital signs, and 12-lead electrocardiograms (ECGs).
- A Data and Safety Monitoring Board (DSMB) has been appointed to this study. The DSMB will monitor the safety of the participants and the scientific integrity of the study.

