4.3. Justification for Dose

The dose regimens selected for this study are provided in Section 4.1.

The selection of dosing regimens was based on the non-clinical and clinical data on mechanism of action of MORF-057, the PK and PD properties, and the safety profile in healthy subjects. In Studies MORF-057-101 and CCI [REDACTED] and based on PK-PD modeling, which included PK and PD assessments in healthy adults, separation of exposures was observed/simulated at low (100 mg once a day – morning [Q.D.-M]), mid (100 mg B.I.D.), and high (200 mg B.I.D.) doses, and maximum saturation of $\alpha 4\beta 7$ receptor occupancy was observed following 100 mg B.I.D. and 200 mg B.I.D. doses. It is expected that $\alpha 4\beta 7$ receptor occupancy will be approximately 70% at trough level following 100 mg Q.D.-M dosing. MORF-057 exhibited favorable and near dose-proportional PK across doses with only mild, non-serious AEs reported that did not result in study drug discontinuation. The plasma exposure (AUC), peak (Cmax) and trough (Ctrough) concentrations across selected dosing regimens would help to study dose-response and exposure/concentration response relationships. This exposure was seen in healthy individuals and is expected to be similar in patients with UC to provide levels that would achieve the intended efficacy and safety.

MORF-057 is designed specifically to inhibit $\alpha 4\beta 7$, which is involved in the trafficking of immune cells to sites of inflammation in the intestinal mucosa but exhibits low inhibition of all other integrins, including $\alpha 4\beta 1$. Integrin $\alpha 4\beta 1$ regulates immune cell trafficking to many non-mucosal tissue sites including skin, lung, and the central nervous system (von Andrian 2000). In human whole blood ex vivo studies, the selectivity ratio of IC50 and IC90 values with respect

to $\alpha 4\beta 7$ and $\alpha 4\beta 1$ for MORF-057 are 1:610 and 1:700, respectively. The MORF-057 doses selected for the current study are anticipated to cause minimal to no $\alpha 4\beta 1$ inhibition in humans, and $\alpha 4\beta 7$ and $\alpha 4\beta 1$ receptor occupancies in blood will be assessed as an exploratory endpoint.

The International Council for Harmonisation (ICH)E4 guidelines as well as the Guideline on the development of new medicinal products for the treatment of UC (CHMP/EWP/18463/2006 Rev.1) accept placebo as an acceptable comparator (monotherapy or add-on to established therapy) in clinical trials.

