 - Agrees to use a male condom, with female partner use of an additional highly effective contraceptive method with a failure rate of $<1\%$ per year (as described in Section 10.5.3) when having sexual intercourse with a woman of childbearing potential who is not currently pregnant.

- b. A female participant is eligible to participate if she is not pregnant or breastfeeding, and one of the following conditions applies:

- Is a woman of non-childbearing potential (as defined in Section 10.5.1)

OR

- Is a woman of childbearing potential (as defined in Section 10.5.1) and agrees to use a contraceptive method that is highly effective with a failure rate of $<1\%$ per year (as described in Section 10.5.2) during the study Treatment Period and for at least 28 days after receiving the last dose of MORF-057

Note: For contraception requirements on or after Protocol Amendment Version 3.0, see Section 10.5.2.2.

11. For the study Treatment Period and at least 14 days after receiving the last dose of MORF-057, male participants must agree not to donate sperm and female participants must agree not to donate eggs (ova, oocytes).

Informed Consent

12. Capable of giving signed informed consent, as described in Section [10.1.4](#), which includes compliance with the requirements and restrictions listed in the ICF and in this protocol

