10.5.2. Contraception Guidance for Female Study Participants

10.5.2.1. Female Study Participants Who **Do Not** Consent to Dose Switch in LTE Period

Note: This is relevant for participants who **do not** consent to the dose switch in the LTE Period. For contraception requirements for those who **do** consent to the dose switch in the LTE Period, see Section 10.5.2.2.

CONTRACEPTIVES ^a ALLOWED DURING THE STUDY INCLUDE:	
Highly Effective Methods^b Failure rate of <1% per year when used consistently and correctly.	
• Implantable progestogen-only hormone contraception associated with inhibition of ovulation ^c + 1 physical barrier method ^d	
• Intrauterine device (IUD)	
• Intrauterine hormone-releasing system (IUS) ^c + 1 physical barrier method ^d	
• Bilateral tubal occlusion/ligation	
• Azoospermic partner (vasectomized or due to a medical cause)	
Azoospermia is a highly effective contraceptive method provided that the partner is the sole sexual partner of the woman of childbearing potential and the absence of sperm has been confirmed. If not, an additional highly effective method of contraception should be used. Spermatogenesis cycle is approximately 90 days.
 
Note: documentation of azoospermia for a male participant can come from the site personnel's review of the participant's medical records, medical examination, or medical history interview.

• Combined (estrogen- and progestogen-containing) hormonal contraception associated with inhibition of ovulation ^c (listed below) +1 physical barrier method ^d	
 –oral –intravaginal –transdermal –injectable

 • Progestogen-only hormone contraception associated with inhibition of ovulation^c+1 physical barrier method^d 
 –oral –injectable • Sexual abstinence

Sexual abstinence is considered a highly effective method only if defined as refraining from heterosexual intercourse during the entire period of risk associated with the study treatment. The reliability of sexual abstinence needs to be evaluated in relation to the duration of the study and the preferred and usual lifestyle of the participant.

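### The embryo-fetal margins in Section 2.2.1 cannot be right in the order printed; separately, the protocol both rejects and lists systemic hormonal contraception for women who do not switch dose

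*Protocol*

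**What the plan says.** **Margins.** Section 2.2.1 gives four animal-to-human margins, each for 100 and 200 mg B.I.D.:

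- Gastric changes, 26-week study: "50 mg/kg/day) is 8.2 -fold or 4.1-fold, respectively".
- Dog NOAEL, 39-week study: "300 mg/kg/day) is 190.2-fold or 95.6-fold for the 100 or 200 mg B.I.D. doses, respectively".
- Dog dose with minimal transaminase rises: "approximately 20-fold for the 100 mg B.I.D. and 10-fold for the 200 mg B.I.D. doses".
- Rabbit embryo-fetal NOAEL: "The safety margin based on the embryo-fetal NOAEL in rabbits (50 mg/kg/day) is 0.8-fold or 1.6-fold for the 100 or 200 mg B.I.D. doses", with the word respectively following.

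Section 4.3 adds that "MORF-057 exhibited favorable and near dose-proportional PK across doses".

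**Contraception.** Section 2.3.2.1, in the paragraph on CYP3A induction, says that "systemic hormonal contraception should not be considered reliable and should not be used for the purpose of contraception". No dose or participant group is named. Section 10.5.2.1, for women who do not consent to the LTE dose switch, includes among its highly effective methods "Combined (estrogen- and progestogen-containing) hormonal contraception associated with inhibition of ovulation" together with one physical barrier method. Progestogen-only and implantable hormonal methods are listed on the same terms. Section 10.5.2.2, for women who do switch, classes systemic hormonal methods as ineffective and does not permit them. The note under the female part of inclusion criterion 10 (Sections 1.1 and 5.1) reads: "For contraception requirements on or after Protocol Amendment Version 3.0, see Section 10.5.2.2".

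**The concern.** The rabbit pair moves in the opposite direction to every other pair in its paragraph. As printed, the dose that Version 3.0 offers in the LTE has the larger embryo-fetal margin. It is also the only margin of the four close to 1-fold, so an error of order or value matters more here than it would at 95-fold.

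Section 2.3.2.1 describes the gastric, hepatic and hematopoietic findings as at least partly reversible and generally open to clinical monitoring. It says no such thing of embryo-fetal effects. For that risk the protocol relies on excluding pregnancy and on contraception. Both the margin and the contraception text therefore need to be coherent, and each has a separate fault. The two faults concern different groups and have different remedies.

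**Working it through.** **1. The margins**

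Margin = animal exposure at the reference dose / human exposure at the clinical dose. The numerator is the same for both clinical doses, so

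margin(200) / margin(100) = human exposure(100) / human exposure(200).

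With near dose-proportional PK (Section 4.3) this ratio should be about 0.5. From the figures in Section 2.2.1:

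| Margin | 100 mg B.I.D. | 200 mg B.I.D. | Ratio 200:100 | Implied exposure ratio 200:100 |
|---|---|---|---|---|
| Gastric, 26-week | 8.2 | 4.1 | 4.1/8.2 = 0.500 | 2.00 |
| Dog NOAEL, 39-week | 190.2 | 95.6 | 95.6/190.2 = 0.503 | 1.99 |
| Dog transaminases | 20 | 10 | 10/20 = 0.500 | 2.00 |
| Rabbit embryo-fetal | 0.8 | 1.6 | 1.6/0.8 = 2.000 | 0.50 |

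The first three rows say that exposure at 200 mg B.I.D. is about twice that at 100 mg B.I.D. The last row says that it is half. Both cannot hold.

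If the true ratio is about 0.5, three simple repairs fit:

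- The order is transposed: 1.6 at 100 mg B.I.D. and 1.6 × 0.5 = 0.8 at 200 mg B.I.D.
- The 0.8 at 100 mg B.I.D. is right: 0.8 × 0.5 = 0.4 at 200 mg B.I.D.
- The 1.6 at 200 mg B.I.D. is right: 1.6 / 0.5 = 3.2 at 100 mg B.I.D.

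The margin at 200 mg B.I.D. is then 0.4, 0.8 or 1.6. The rabbit and human exposures that would settle it are not in the protocol. A text-extraction fault is unlikely, because the Version 3.0 summary of changes prints the pair in the same order.

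**2. The contraception text**

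| Participant | Section 2.3.2.1 | Group rule in Section 10.5.2 | Consistent? |
|---|---|---|---|
| Woman who switches to 200 mg B.I.D. | systemic hormonal methods not to be used | 10.5.2.2: not permitted | yes |
| Woman who does not switch | systemic hormonal methods not to be used | 10.5.2.1: listed as highly effective, with a barrier | no |

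The Section 2.3.2.1 statement cannot simply be read as meant for switchers. Section 2.2.2 reports weak CYP3A induction at 100 mg B.I.D., which is the regimen that Groups 1 and 2 keep if they do not switch (Section 4.1).

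The criterion 10 note sends all requirements under Version 3.0 to Section 10.5.2.2. The opening lines of that section limit it to switchers and refer everyone else back to Section 10.5.2.1.

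**The case against.** **On the margin.** Nothing in the protocol's rules rests on 0.8 or 1.6. The benefit-risk text in Section 2.3 cites no margin, it names embryo-fetal development as a potential risk without qualifying by dose, and it says that effects in pregnancy are unknown. The contraception rule at 200 mg B.I.D. is the stricter of the two, so it does not follow the inverted figure. Readers are referred to the Investigator's Brochure. All of this stands and limits the consequence. It does not make the printed pair possible.

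A reader might go further and infer that the 200 mg B.I.D. margin is really below 1-fold, or that the inversion decides which dose is below 1. The documents do not support that. Under the three repairs, one dose, both doses or neither dose falls below 1.

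**On contraception.** Section 2.3.2.1 is risk narrative and the same section defers to Section 10.5 for the requirements. Different rules for different dose groups are not an error, and Section 2.2.2 expects greater induction at higher doses. Criterion 10 also cites Section 10.5 as a whole, and a non-switcher who follows the note is sent on to Section 10.5.2.1. The routing is therefore clumsy but does not leave her without a rule. What remains is that the narrative tells every woman not to use a method that her own group's table lists as highly effective. The added barrier does not remove that conflict.

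Three wider readings are tempting and fail:

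- The conflict does not bear on re-consent to the switch, because for switchers Sections 2.3.2.1 and 10.5.2.2 agree.
- It does not reach every non-switching woman of childbearing potential, because Section 10.5.2.1 also lists non-hormonal options such as an IUD, tubal occlusion and abstinence.
- The hormonal methods in Section 10.5.3 are not a contradiction, because they concern partners who do not take the study drug.

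**Conclusion.** Both faults are in the current Version 3.0 text.

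The rabbit embryo-fetal pair is wrong as ordered: its 200:100 ratio is 2.0 against about 0.5 for the other three pairs, a 4-fold discrepancy. This rests on a common numerator for the two doses and on near dose-proportional PK, which Section 4.3 states and the other pairs bear out. The range of 0.4 to 1.6 at 200 mg B.I.D. further assumes that at least one printed value is correct for its dose, or that the two were transposed. Which value is wrong cannot be determined from the protocol.

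The contraception conflict is real but narrow: non-switching women of childbearing potential who use systemic hormonal methods. The protocol does not say how many there are.

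Whether any consent form repeats the margins is unknown, since none is available. No sample size, power or error rate is affected. The points still merit correction because a safety figure for the dose offered in the amendment cannot be right as printed, and because contraception is a stated safeguard for this risk.

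**What to change.** 1. Check the rabbit embryo-fetal margins at both doses against the Investigator's Brochure, correct Section 2.2.1, and check any participant-facing text that repeats the figures. The cost is a source check and a wording correction.

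2. Reconcile Section 2.3.2.1, the criterion 10 note (Sections 1.1 and 5.1) and Sections 10.5.2.1 and 10.5.2.2 so that each group meets one consistent statement and is pointed to the section that applies to it. Which rule applies is a matter for the sponsor's clinical and safety staff; this review does not prescribe one. The cost is more than editorial if the outcome changes the stated requirement for non-switchers, because sites and affected participants would then have to be told.

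The two corrections are independent and can be made separately.

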2.2.2. Clinical Findings

Collectively from 7 Phase 1 MORF-057 studies conducted in healthy participants (N=171 who received MORF-057 across all 7 studies), MORF-057 was well tolerated. There were no deaths or serious adverse events (SAEs).

Drug-drug interactions (DDI) were also evaluated in the Phase 1 clinical program. At a dose of 100 mg B.I.D., MORF-057 is a weak inducer of cytochrome P450 3A (CYP3A). Although other doses have not been assessed for CYP3A induction, higher doses likely carry the risk of greater induction. MORF-057 is also a substrate of hepatic transporters organic anion transporting polypeptide (OATP) 1B1/3 and a sensitive substrate of CYP3A.

Safety data are also available from the completed 52-week Treatment Period in the open-label Phase 2a study, MORF-057-201 (N=39) and from the 12-week Induction Period in this ongoing placebo-controlled Phase 2b study, MORF-057-202 (N=280). Overall, the treatment with MORF-057 was well tolerated in participants with moderately to severely active UC.

- No death occurred in any of the completed or ongoing studies.
- In the Phase 2b study, 5 participants who received either MORF-057 or placebo reported at least 1 serious treatment-emergent adverse event (TEAE), all in Study MORF-057-202. The Investigator considered that none of these serious TEAEs were related to the study drug.
- In the Phase 2 studies, a total of 11 participants discontinued the study treatment due to TEAEs, with 6 MORF-057 treated participants in Study MORF-057-201 and 5 participants who received either MORF-057 or placebo in Study MORF-057-202.
- The most frequently reported TEAEs in participants receiving MORF-057 at any dose in the Phase 2 studies included ulcerative colitis, anemia, nasopharyngitis, and headache.
- No cases of Progressive Multifocal Leukoencephalopathy (PML) were reported in any of the completed or ongoing studies.

The observed safety profile was consistent with the class safety profile for $\alpha 4\beta 7$ integrin inhibitors.

No safety signals have been identified in any of the MORF-057 clinical studies.

The clinical efficacy of MORF-057 has been evaluated in UC patients in the open-label Study MORF-057-201. In this study, a statistically significant decrease in Robarts Histopathology Index (RHI) Score from baseline to Week 12 was achieved, as well as a reduced modified Mayo Clinic Score (mMCS) from baseline. Additionally, a 25.7% remission rate was demonstrated based on mMCS.

In the 12-week Induction Period analysis for this ongoing placebo-controlled Phase 2b study, MORF-057-202, the primary and secondary objectives of clinical remission and clinical response, respectively, were not achieved. A dose-response was observed between the 3 active doses, and 200 mg B.I.D. was the clinically most active dose.

Refer to the current IB for details on the clinical studies conducted to date.

